## **Consultant Arrangements**

Biostatistics support will be provided by [name] from the biostatistics core. The presented statistics and power analysis was developed with [name]. A specialized lab will provide blood level measurements of losartan and its metabolites in the blood ([name] at the University of Florida).

## **Data management**

Data collected will include demographics, clinical symptoms, CFQ-R, pulmonary function tests and NPD. Samples to be collected include nasal fluid (Leukosorb) and nasal cells at the beginning, during and at the end of the study. We will obtain blood for safety reasons (liver and renal function), for evaluation of an inflammatory marker (CBC w/ differential; CMP; CPK, CRP and other inflammatory markers). Blood for levels of losartan and metabolites (before next morning dose) will be also collected at the end of each treatment phase.

No personal identifiers will be collected and each patient's data will be coded. Data will be captured at secure password protected website (Red-Cap). Sites will be granted access to this database.

Monitoring will be provided by Clinical Research Operations & Regulatory Support (CRORS) monitoring group at the University of Miami.

## **Potential Risks**

All procedures are performed during this study are routine procedures and are associated with minimal risks.

Pulmonary Function Testing (Spirometry) is a routine clinical procedure with few risks. Patients are coached to make repeated forceful breathing efforts. The subjects might have chest soreness. Unusually, subjects may become lightheaded during these efforts. We will minimize this risk by having the PFT done in a sitting position.

NPD measurement: is a non-invasive method with minor risks and will be performed according to standard procedures (21-25).

Minor risks include swallowing and aspiration of the solution used for rinsing the nose. Having the patient bending the head forward will minimize this risk, so that the solution is dripping out of the nose and not in the pharynx. The perfusion rate will be set at 5 ml/min, indicating that the nose will be rinsed with low volumes. Even in case of accidental swallowing or aspiration, there are limited risks of a severe reaction, even in a respiratory-wise impaired individual. Amiloride is a diuretic medication and can increase urine production when given in a higher dose, which is not expected here as the used dose is low and systemic absorption is not anticipated. Isoproterenol is a  $\beta$ -mimetic and can lead to tachycardia, hypertension and migraine. The dose used is low and the systemic absorption negligible. Other potential side effects include nosebleed, runny nose and coughing. For the study, a subcutaneous insertion of a butterfly needle is required, which brings a minimal risk of bruising, bleeding and infection. The butterfly is only used as a control electrode. No medications are injected through it into the skin or vascular system.

Nasal sample collection and cell sampling: this procedure is routine and is sometimes associated with an unpleasant feeling due to the use of the Leukosorb filter, itching and coughing. Cell sampling can cause a mild discomfort and a mild nosebleed due to brushing.

Phlebotomy: The risks from blood draw from a vein are minimal but include discomfort at the site of puncture, possible bruising around the puncture site, rarely an infection, and uncommonly, fainting from the procedure. Blood draws will be performed with as much care as possible to minimize local complications. Subjects will be sitting during the process for their comfort and will be asked not to look directly at the site of blood draw.

Treatment with losartan (IND exemption for CF approved): Losartan is an FDA-approved ARB widely prescribed for treatment of hypertension, heart failure, and for renal protection in patients with diabetes. The doses proposed in this study are well tolerated by non-hypertensive patients without significant effect on blood pressure. The most common side effects are fatigue and dizziness. Serious adverse events that are rare include angioedema, hypotension, renal dysfunction or failure, blood dyscrasias, hepatitis, or rhabdomyolysis (clinical assessment of muscle pain). The following should lower the risks to the subjects: The first dose of medication will be administered in the clinic and the patient observed for two hours with blood pressure monitoring. Subjects with hyperkalemia, renal dysfunction, or who are taking potassium supplements will not be enrolled into the study. Participants will be given written descriptions of potential side effects and what to do. For example, mild postural hypotension can be minimized by getting up slowly and maintaining adequate hydration. Skin rashes, palpitations or other moderate or severe adverse events (interference with usual daily activities) without other clear explanation should warrant immediate cessation of treatment and notification of study personnel. There are no drug interactions between losartan and OrkambiTM. Nor are there relevant drug interactions between losartan and or SymdecoTM (by Vertex' drug interaction guidance in their 661 and later clinical trials).

Sweat chloride collection: this is a routine procedure in a CF center and uses a macroduct to collect sweat secretions stimulated by pilocarpine iontophoresis, done according to CFF and CLSI guidelines. The test is well tolerated. A small risk of complications includes mild reddening of the skin. Damage to the skin, such as blistering or burns, occurs very infrequently and this risk can be minimized by careful attention to technique.

Questionnaires, Health History and Physical Examination acquire information that is routinely collected. No significant physical risks arise from these procedures. There is always the risk of psychological distress and breach of confidentiality. In order to minimize this risk, electronic medical records are held in HIPAA compliant password-protected databases, and written information is stored in locked files or file-rooms when not attended by study personnel.

### Pregnancy

Female subjects will have to adhere to strict birth control. They will be counseled to immediately inform the Investigator if there was non-compliance or if pregnancy occurs during study treatment and within 90 days after the last dose of the study drug.

If a female subject becomes pregnant while participating in the study, study drug must be immediately and permanently discontinued. Positive pregnancy test results, for minors under the age of 18, will be shared with parents. The subject will be counseled and if pregnancy is continued until delivery, the subject if followed and the infant for 1 year after the birth, provided informed consent/assent is obtained. A separate informed consent form will be provided

to explain these follow-up activities. The investigator must notify the DSMB and IRB within 24 hours of the site's knowledge of the subject's pregnancy and other agencies as by law. Pregnancy itself does not constitute an AE.

## **Adequacy of Protection Against Risks**

Recruitment and Informed Consent: Subjects will be recruited from the respective CF clinics. First, the subjects will be briefed about the study and if interested will be invited to come on a separate day with ample time just to discuss the study objectives, procedure risks and benefits with the study investigators. The study and informed consent form will be approved by the University of Miami's IRB. Subjects will have sufficient time to meet with the co-PIs to address all their questions about the research and take the informed consent home to discuss with family.

Protection against Risk: General approaches for each procedure to minimize risk were described above. We will carefully select subjects that can tolerate the procedures of the study. All participant sites are fully equipped to handle possible fainting and other, more serious types of medical emergencies (CPR cart physicians and study staff are trained in BLS and ACLS) to handle any potential emergency.

All research data will be secured using password in Universities approved databases. Access to these data will be restricted to the research staff only.

**Vulnerable Populations:** The study intends to enroll subjects from the following "vulnerable" categories: minor. In this case, subjects will be asked to sign the IRB approved assent form.

## **Potential Benefits of the Proposed Research to Human Subjects and Others**

Subjects will likely not receive any long-term benefit from participating in this project, but might experience a potential benefit from participating (improved clearance). They always have the alternative not to participate. By participating, they will allow the performance of the proposed studies. The studies have the potential for an overall benefit in advancing knowledge of the disease studied. Because the study drug is usually well tolerated, the risks to subjects are reasonable in relation to the anticipated benefits, including knowledge to be gained.

## **Importance of the Knowledge to Be Gained**

The proposed clinical research has the potential of providing important information that could be used as base for future studies and eventually change the way CF is treated and improving not only the quality of life of patients with CF but also their lung function, at least in combination with other treatments. If the study is negative, we will have gained improved understanding of why and might be able to deliver these kind of medications via a different route *in vitro* and *in vivo*.

## **Communication between sites**

There will be several lines of communications established between the sites. The investigators, Drs. [name], [name], [name] and [name] will have monthly teleconference meetings to set up the study at all sites including use of case report forms (CRFs) and databases; establishing route of communications and shipping by pharmacy etc. When the trial is ongoing the meetings will be at least bi-monthly to discuss the progress of the study and bring up issues that need resolution. More frequent informal communications will occur via email and phone calls if necessary. The conference calls will be attended by additional members of the team as needed to resolve any issues. Cystic Fibrosis Foundation Therapeutics (CFFT) will serve as DMC and DSMB on this study.

## **Safety Reporting and Monitoring Plan**

Data monitoring plans will be implemented as follows:

The study will be monitored by Clinical Research Operations & Regulatory Support (CRORS) monitoring group at the University of Miami.

3. Monitoring will occur every 3 months or more frequently if needed.
4. IND exemption for use of losartan in CF patients was granted by the FDA
5. Safety monitoring will be done by the DSMB of the CFFT.
6. Adverse Event Monitoring

- Subjects will be carefully monitored for adverse events (AEs) and serious adverse events (SAEs). Adverse events will be assessed in terms of their seriousness, severity, and relationship to the administration of Losartan.
- All adverse effects will be reported to the co-PIs and discussed with the monitoring group
  - If deemed severe the data will be shared with the DSMB. They will make the decision whether or not to stop the trial.
  - All SAEs will be reported to the DSMB and the appropriate agencies as required.
  - All adverse effects will be reported according to the rules to the FDA, the IRB and to the DMSB

## Definitions

7. Adverse Event (AE): An AE is any untoward medical occurrence in a clinical study participant administered with a pharmaceutical product. The AE does not necessarily have to have a causal relationship with this treatment. An AE can therefore be any unfavorable and unintended sign (including an abnormal laboratory finding), symptom, or disease temporally associated with the use of an investigational product, whether or not considered related to the medicinal product.
8. Unexpected AE: is any adverse drug event, which is not consistent with the current Losartan US Package Insert.
9. Serious Adverse Event (SAE): A SAE is any untoward medical occurrence that at any dose:
  - results in death
  - is life-threatening
  - requires unanticipated in-patient hospitalization or prolongation of existing hospitalization
  - results in persistent or significant disability or incapacity
  - results in a congenital anomaly or birth defect
  - any significant medical event as per the investigator's discretion

### Relationship of Adverse Event to Losartan

The assessment of the relationship of an AE to the administration of study drug is a clinical decision based on all available information. An assessment of 'No' would include choices of "not related" or "unlikely related" in the following cases:

1. The existence of a clear alternative explanation, or
2. Non-plausibility (clearly an unrelated circumstance).

An assessment of 'Yes' includes choices of "possibly related" or "related" and indicates that there is a reasonable suspicion that the AE is associated with the use of the investigational drug.

Factors to be considered in assessing the relationship of the AE to study drug include:

- The temporal sequence from drug administration: The event should occur after the drug is given. The length of time from drug exposure to event should be evaluated in the clinical context of the event. We will consider a significant time interval up to 2 hours.
- Underlying, concomitant, intercurrent diseases: Each report should be evaluated in the context of the natural history and course of the disease being treated and any other disease the subject may have (i.e. a pulmonary exacerbation)
- Concomitant medication or treatment: The other drugs the subject is taking or the treatment the subject receives should be examined to determine whether any of them might be suspected to cause the event in question
- Concurrent study procedures: Study procedures should also be considered as possible causes of an AE.

In this study, the investigator will make a separate and independent assessment of every AE's relationship not just to the study drug, but also to concurrent study procedures and to the subject's pre-existing medical condition(s).

A laboratory test abnormality considered clinically relevant, e.g., causing the subject to withdraw from the study, requiring treatment or causing apparent clinical manifestations, or judged relevant by the investigator, should be reported as an AE. Each event should be described in detail along with start and stop dates, severity, relationship to investigational product, action taken and outcome.

Each AE should be followed up until resolution or stabilization as determined by the investigator.

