## Study Procedures

Once informed consent is signed, the subjects will undergo the following procedures:

General and questionnaire: Data collected will include demographics, clinical symptoms, CFQ-R, and blood work. We will also collect history of other medical conditions, medications, and exacerbation history.

History and physical examination will be performed including vital signs and body mass index (BMI) will be recorded.

Pulmonary function testing will be performed according to American Thoracic Society recommendations. Participants will be asked to refrain from using short-acting bronchodilator drugs for at least 4 hours before testing and not take any long acting bronchodilator in the morning. Height, weight and oxygen saturation will be measured prior to these tests.

Blood and urine samples: Urine pregnancy test will be performed at all site visits. If positive, confirmation with serum pregnancy test will be obtained. Blood test for liver and renal function, inflammatory markers and blood levels of losartan and the metabolites EXP3179/EXP3174 will be drawn. A total of 30 cc (2 tablespoons) of blood will be collected at Visit 1 and visits 4, 5, and 7.

NPD measurement will be performed according to standard procedures (latest SOP of the Therapeutic Development Network of the CF Foundation). Double lumen nasal catheters with an external diameter of 2.5 mm will be used for measurements. One lumen will be filled with freshly prepared agar; the other lumen will be used for perfusion with different solutions. The agar catheter and subcutaneous bridges (metal butterfly needle system) will be made prior to use by warming 3% agar gel and injecting the solution into the catheter. They will be attached to 3M KCl/calomel reference electrodes (Baxter; Deerfield, IL) and connected to a bioamplifier system (AD Instruments; Colorado Springs, CO) for measuring and recording. The initial potential difference (PD) will be measured at the anterior tip of the inferior meatus. Then, the basal PD will be measured at various distances within the inferior meatus in each nostril. The nasal catheter will be fixed at the most negative potential in one nostril, and the test will be initiated using perfusion

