## List of assessments

VISIT	Visit 1	Visit 2	Visit 3 Phone call	Visit 3.a Phone call	Visit 4	Visit 5	Visit 6 Phone call	Visit 7	Visit 8
	-1 weeks	25 mg or 50 mg losartan/placebo	50 mg or 100 mg losartan/placebo	1 week ± 2 days	2 days ± 1 day from Visit 3	3 weeks ± 2 days	6 weeks ± 2 days	10 weeks ± 2 days	13 weeks ± 2 days
Informed consent	X								
Full medical history	X								
Intermittent history		X			X	X		X	X
Physical exam	X	X			X	X		X	X
Vitals	X	X			X	X		X	X
Pulse oximetry	X	X			X	X		X	X
Concomitant medications	X								
Changes in medications		X	X	X	X	X	X	X	X
CFQ-R	X					X		X	
Review adverse events, exacerbations		X	X	X	X	X	X	X	X
Spirometry	X					X		X	
CBC w/ differential; CMP; CPK, CRP and other inflammatory markers	X				X	X		X	
Blood for levels of losartan and metabolites (before next morning dose)						X		X	
NPD	X					X		X	
Leukosorb cytokine levels		X							X
Nasal cells		X							X
Sweat chloride		X							X
Serum or urine pregnancy test	X	X			X	X		X	X

IP dispensation: Visit 2 (3-week supply), visit 4 (3-week supply) and visit 5 (8-week supply)

## Appendix 2

CFQR Questionnaire:

More information:

<http://qol.thoracic.org/sections/instruments/ae/pages/cfq-cfq-r.html>

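### The relatedness criteria name 2 hours as the significant interval without giving it a scope, which does not fit the instruction to judge latency in context or a 13-14 week oral treatment

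*Combined protocol and SAP*

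**What the plan says.** The section Relationship of Adverse Event to Losartan makes relatedness a judgement that "is a clinical decision based on all available information". It lists timing as one of four factors. Two sentences in the timing item matter here. One leaves latency open: "The length of time from drug exposure to event should be evaluated in the clinical context of the event". The sentence that comes straight after it puts a number on latency: "We will consider a significant time interval up to 2 hours".

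The second carries no restriction to the first dose, to acute reactions or to any part of the treatment period. The section applies to every adverse event, and it brings laboratory findings in: "A laboratory test abnormality considered clinically relevant" is to be reported as an adverse event.

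The Potential Risks section names angioedema, hypotension, renal dysfunction or failure, blood dyscrasias, hepatitis and rhabdomyolysis as rare serious harms of losartan. It also describes a two-hour clinic observation after the first dose. The relatedness section does not refer to that observation.

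**The concern.** The first timing sentence sets no fixed limit. The second supplies the only number. An investigator who wants a working rule will find 2 hours and nothing else, for a drug taken once and then twice daily for about 13-14 weeks. Several of the listed harms are of a kind found on blood tests, not by watching a patient after a dose.

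What is at stake is the coding of relatedness. The Safety Reporting and Monitoring Plan requires each adverse event to be assessed for its relationship to losartan. The Intervention section ties a discretionary decision at the end of week 1 to whether an adverse event is related to study medication. Four sites of about 9 patients each could also settle the tension between the two sentences in different ways.

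**Working it through.** The plan gives no derivation of the 2 hours, so there is no figure to reproduce. The check sets the named interval against the timing that the protocol's own safety schedule can deliver.

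**Inputs**

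- Blood draws (Study Procedures): "A total of 30 cc (2 tablespoons) of blood will be collected at Visit 1 and visits 4, 5, and 7". Appendix 1 places the blood count, metabolic panel and CPK at the same four visits.
- Visit spacing (Appendix 1): "IP dispensation: Visit 2 (3-week supply), visit 4 (3-week supply) and visit 5 (8-week supply"). The week labels do not line up cleanly with the visit columns in the copy read, so the supply line is used to place the visits: Visit 4 at week 3 and Visit 5 at week 6. The supplies sum to 3 + 3 + 8 = 14 weeks, which matches the stated total duration.
- Visit windows (Appendix 1): plus or minus 2 days.
- Dosing (Intervention): once daily for 1 week, then twice daily.

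**Shortest gap between scheduled draws**

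1. Visit 1 to Visit 4: 1 week of screening + 3 weeks = 4 weeks.
2. Visit 4 to Visit 5: 6 − 3 = 3 weeks, the shortest. 3 × 7 × 24 = 504 hours.
3. With both windows: 21 − 4 = 17 days, 17 × 24 = 408 hours; 21 + 4 = 25 days, 25 × 24 = 600 hours.
4. Visit 5 to Visit 7 is longer: with Visit 7 at week 13, 13 − 6 = 7 weeks.

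**What that means for a 2-hour interval**

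An abnormality absent at Visit 4 and present at Visit 5 began at some unknown time within about 504 hours, during which about 21 × 2 = 42 doses were scheduled. The protocol does not say whether time from exposure runs from the first dose or the most recent one, and the 2-hour interval works on neither reading:

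- From the first dose: the first on-treatment draw comes about 3 weeks (504 hours) later, so no finding on scheduled blood can be placed within 2 hours of it.
- From the most recent dose: the onset is not known closely enough to say which dose preceded it, or by how long.

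So for renal, blood, liver or muscle findings first seen on scheduled blood, the one interval the criterion names cannot be applied. These figures describe timing resolution only. They are not a misclassification rate, and none can be derived from the documents.

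**Where the sentence can have an effect**

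- Relatedness assessment of every adverse event: yes.
- Week-1 step: yes, for symptoms. No blood is scheduled between Visit 2 and Visit 4, so laboratory findings do not enter there.
- Adverse event recording: no. The definition requires no causal link.
- Serious adverse event reporting to the DSMB: no. All are reported.
- Endpoints and statistical analysis: no. None counts related events.

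**The case against.** The strongest reply is that the sentence is harmless in its setting. Timing is one of four factors. A negative answer is tied to a clear alternative explanation or non-plausibility, and a positive one needs only that "there is a reasonable suspicion that the AE is associated with the use of the investigational drug". The two sentences can even be read together: judge latency in context, and treat an event within 2 hours as a notable temporal signal. The unknown onset of laboratory findings also comes from the sampling schedule and would remain under any wording.

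Much of this stands, and it is why the point is minor. It does not remove the point. The harmonising reading is possible, but the text does not state it. A factor that investigators are told to weigh should not give one open instruction and one fixed number with no scope. That onset cannot be timed to hours is a reason not to name an interval in hours as a general criterion.

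Some stronger readings are tempting, and the documents do not support them:

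- *Events after 2 hours must be coded as not related.* Two hours is the only interval named, but it is not said to be exclusive, and the other tests in the section limit its weight.
- *The 90-day pregnancy reporting period contradicts the 2 hours.* That period governs when a pregnancy must be notified. It is not a time from dose to event, so the two are not comparable.
- *Hours since a home dose are never recorded.* The section asks for "Each event should be described in detail along with start and stop dates, severity, relationship to investigational product, action taken and outcome", which mentions dates only. The case report forms are not in the documents and may capture clock times.
- *The 2 hours comes from the first-dose observation.* This is plausible but unstated. The summary of changes for version 2.0 also mentions a 2-hour post-dose drug-level sample, but a change log cannot settle the meaning of the current text.

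**Conclusion.** The point holds as a minor inconsistency in a stated safety criterion. An unscoped 2-hour interval sits directly after an instruction to judge latency in context. It does not fit a treatment of about 13-14 weeks whose listed harms may first appear on blood drawn at least about 3 weeks apart (17 days at the closest the windows allow). Read literally, it lowers the weight given to later events in the relatedness assessment and in the week-1 discretionary step.

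The conclusion assumes that some investigators would read the sentence literally, and that some laboratory events would first be seen at scheduled draws and not at an unscheduled visit. No misclassified event is shown. A reader should not infer that safety reporting or the trial's efficacy results are compromised, since neither uses the 2-hour sentence.

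**What to change.** Reconcile the two timing sentences in the relatedness section, together with the first-dose observation in Potential Risks if that is the source of the 2 hours. After the change, the 2-hour interval should either carry an expressly stated scope or no longer stand as a general criterion of relatedness. This review proposes no alternative interval; what the sentence was meant to cover is for the sponsor and investigators to state.

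The cost is a one-sentence amendment, passed to all four sites so that coding is consistent. The possible downside is that more events are coded as possibly related. The documents give no basis for estimating how many.
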